# 1.1 Study design

The core study (A2203) was planned as a randomized, double blind, placebo controlled, parallel group, 5-arm study in at least 360 subjects with moderate to severe Atopic Dermatitis (AD). Unbalanced randomization ratio was used, intending to result in approximately 90 subjects randomized in each of the 30 mg/day and 50 mg/day dose arms as well as in the placebo arm, and 45 subjects in each of the 3 mg/day and 10 mg/day arms. The randomization was stratified by baseline severity of atopic dermatitis (IGA score moderate or severe) and by geographical region.

The possibility to perform an interim analysis (IA) in order to support decision making concerning the current clinical study or project was addeded to the protocol in V3. This interim analysis was performed in May 2020 on 187 patients who had completed week 16 or discontinued before this timepoint. Based on the results from this IA, it was decided to stop both the core and extension studies for reasons of lack of efficacy and thus the final number of patients, and follow-up time per patient is less than planned in the protocol.

The core study (A2203) consisted of a screening period of up to 4 weeks (depending on current medication use and associated washout period), and a 16-week double blinded treatment period. The primary endpoint was to be assessed at the end of the 16 week treatment period.

After the end of treatment visit, subjects were offered the possibility of ongoing treatment in the extension study (A2203E1), or of entering the 4 week treatment-free follow up period.

[figure not shown]

The extension study (A2203E1) was intended to be a randomized, double blind, parallel group, 2-arm study in up to approximately 202 to 230 subjects. This number assumed a discontinuation rate of 15% to 25% in the core study (A2203)

In the extension study, subjects who had received ZPL389 30 mg o.d. or 50 mg o.d. doses in the core study, would continue to receive the same doses in a double-blinded fashion. Subjects who had received ZPL389 3 mg, 10 mg or placebo in the core study, would be randomized to receive ZPL389 30 mg o.d. or 50 mg o.d. in a 1:1 ratio. All subjects would receive concomitant or intermittent topical corticosteroids (TCS) and/or topical calcineurin inhibitors (TCI) along in a standardized regimen with ZPL389.

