# Table 1-2Objectives for the extension study A2203E1

Objectives	Endpoints

[figure not shown]
Included in CSR?

Primary objective

Novartis F	or business use only
SAP	

Page 11 CZPL389A2203

Objectives	Endpoints	Included in CSR?
To assess the short-term and long- term safety of 30 mg o.d and 50 mg o.d ZPL389 with concomitant or intermittent use of TCS and/or TCI up to total of 32 weeks and 116 weeks of treatment.	Frequency of AEs at Week 32 (short- term) and Week 116 (long-term).	Yes
Secondary objectives		
To evaluate the efficacy of 30 mg o.d and 50 mg o.d ZPL389 with concomitant or intermittent use of TCS and/or TCI as assessed by IGA response over time.	IGA score over time (absolute and relative frequencies from core study baseline).	Yes
To evaluate the efficacy of 30 mg o.d and 50 mg o.d ZPL389 with concomitant or intermittent use of TCS and/or TCI as assessed by EASI	EASI score over time (absolute and percent change from core study baseline).	Yes

Novartis SAP	For business use only	Page 12 CZPL389A2203
Objectives	Endpoints	Included in CSR?

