# 2.3 Patient disposition, demographics and other baseline characteristics

# 2.3.1 Patient disposition

Patient disposition will be summarized based on the randomization set and will focus on showing the number of patients enrolled and the times at which they discontinued the study, including how many progressed to the extension study and how many did not. Data will be summarised by treatment group to determine whether discontinuation rates and reasons were similar across groups.

The key focus is on enrolment and discontinuation during the core study. Subject disposition in the extension is unlikely to be as intended due to the early stopping of the trial.

Since part of the study was conducted during the COVID-19 pandemic summary tables will also indicate how many patients were enrolled and completed the trial during the pandemic time period.

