# 2.7.1 Adverse events (AEs)

Adverse events will be coded according to the MedDRA dictionary. The actual MedDRA version used for reporting the adverse events will be described in a footnote of the CSR tables.

Only treatment emergent AEs will be presented. Treatment emergent adverse events are those events that

- started after the first dose of study treatment, or
- were present prior to the first dose of study treatment but increased in severity based on preferred term.

AEs observed four weeks or more after last study treatment intake will not be considered as treatment-emergent.

The purpose of the AE summaries are to understand what AEs are reported within different time periods relative to start of treatment. Thus AEs will be summarized for different time periods to cover the core and extension studies. Since AEs reported in a period may also be affected by AEs in any previous periods of treatment, the treatment groups for periods after 16 weeks will separate subjects who received placebo and the lower ZPL389 doses for the first 16 weeks of their treatment from those who had already received 30mg or 50mg ZPL389 for 16 weeks.

Therefore AEs will be summarized across the following time periods

- AEs with onset date during the first 16 weeks of treatment where treatment group is the treatment group in the core study. This summary will be based on the full safety set.
- AEs with onset date after week 16 but before week 32 of study treatment. This summary will be based on the subset of the safety set comprised of patients who have on study treatment data after week 16. Treatment groups for this summary are
  - 1. Placebo and low dose ZPL389 followed by 30mg ZPL389 (for subjects who received placebo 3mg or 10mg ZPL389 in the core study)
  - 2. Placebo and low dose ZPL389 followed by 50mg ZPL389 (for subjects who received placebo 3mg or 10mg ZPL389 in the core study)
  - 3. 30mg ZPL389 (for subjects who received 30mg ZPL389 in the core study)
  - 4. 50mg ZPL389 (for subjects who received 50mg ZPL389 in the core study)
- AEs with onset date after week 32 of study treatment. This summary will be based on the subset of the safety set comprising patients who have on study treatment data after week 32. By week 32 it is expected that the treatment received in the core study will have less direct influence and therefore treatment groups for this summary are
  - 1. 30mg ZPL389
  - 2. 50mg ZPL389

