AE summaries will show, for each treatment group, the number and percentage of subjects

- having any AE,
- having an AE in each primary system organ class
- having each individual AE (preferred term).

Summaries will also be presented for AEs by severity and for study treatment related AEs.

If a subject reported more than one adverse event with the same preferred term, the adverse event with the greatest severity will be presented. If a subject reported more than one adverse event within the same primary system organ class, the subject will be counted only once with the greatest severity at the system organ class level, where applicable.

AEs leading to discontinuation of the study drug will be summarized in a similar way.

Serious adverse events will also be summarized.

Separate summaries will be provided for deaths, serious adverse events, and other significant adverse events leading to discontinuation.

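### The available SAP text keeps AE frequency to Week 32 and Week 116 as the extension's primary endpoint, but plans only crude percentages in three windows that cannot be added, the last of them dependent on length of follow-up

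*SAP*

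**What the plan says.** SAP Table 1-2 gives the extension's primary objective as short-term and long-term safety of 30 mg and 50 mg "up to total of 32 weeks and 116 weeks of treatment". The endpoint is "Frequency of AEs at Week 32 (short- term) and Week 116 (long-term"), and the table marks it as included in the study report.

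SAP 2.7.1 then sorts treatment-emergent AEs by onset into three windows:

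- "AEs with onset date during the first 16 weeks of treatment where treatment group is the treatment group in the core study", on the full safety set and by core treatment group.
- "AEs with onset date after week 16 but before week 32 of study treatment", on subjects with on-treatment data after Week 16, in four groups that keep switched subjects apart from those on 30 mg or 50 mg from the start.
- "AEs with onset date after week 32 of study treatment", on subjects with on-treatment data after Week 32, in two groups (30 mg, 50 mg) that merge continuous and switched subjects.

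The statistic is the same in each: "AE summaries will show, for each treatment group, the number and percentage of subjects" with any AE, with an AE in each organ class, and with each preferred term.

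On follow-up, SAP 1.1 says that after the stop "the final number of patients, and follow-up time per patient is less than planned in the protocol", and SAP 2.3.1 says "Subject disposition in the extension is unlikely to be as intended due to the early stopping of the trial". SAP 2.4.1 derives exposure in days and years and tabulates thresholds up to 2 years, but does not use exposure as an AE denominator. SAP Section 4 lists two changes, to adjudication and to MCP-Mod; neither concerns AE reporting or the Week 116 horizon.

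**The concern.** The objective is cumulative, but the tables are split by period. A subject with an AE in more than one window counts in each, and each window has its own denominator, so the percentage with an AE by Week 32 cannot be recovered from the first two tables. This is so even for subjects on 30 mg or 50 mg from Day 1.

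The window after Week 32 has a second problem. It has no upper limit, and any on-treatment data past Week 32 admits a subject. Someone treated briefly past that point weighs as much in the denominator as someone treated for many months. When follow-up is cut short, the percentage falls although the risk per unit of time has not changed. A reader could take a low late figure as long-term reassurance, or set it against the 16-week core figure, when it may reflect short observation only.

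**Working it through.** The documents give no expected AE frequency, power or precision for this endpoint, so there is no plan figure to reproduce. The check uses the SAP's time horizons and an assumed AE rate.

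**1. Can the windows be added?** Suppose 40% have an AE in Weeks 0-16 and 30% in Weeks 16-32, on one common denominator (illustrative). The percentage with an AE by Week 32 lies between max(40, 30) = 40% and 40 + 30 = 70%. Under independence it is 1 - 0.60 × 0.70 = 58%. The planned denominators also differ, so the real tables are less informative still.

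**2. How far does the post-Week-32 percentage depend on follow-up?** The planned length of that window is 116 - 32 = 84 weeks. Assume a constant first-event rate r = 0.20 per patient-year, which is not in the documents. If follow-up is spread evenly from 0 to T, the expected crude percentage is 1 - (1 - exp(-rT))/(rT).

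- T = 16 weeks: rT = 0.20 × 112/365.25 = 0.0613, giving 3.0%.
- T = 40 weeks: rT = 0.20 × 280/365.25 = 0.1533, giving 7.3%.
- T = 84 weeks: rT = 0.20 × 588/365.25 = 0.3220, giving 14.5%.

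The ratio is 14.5/3.0, or about 4.8. The exposure-adjusted rate is 20 per 100 patient-years in all three cases. For other assumed rates (52-week year):

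| Rate per patient-year | 0-16 weeks | 0-40 weeks | 0-84 weeks |
|---|---|---|---|
| 0.25 | 3.7% | 9.0% | 17.7% |
| 1.0 | 13.9% | 30.2% | 50.4% |

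**3. What would the stated endpoint be?** At r = 0.20, cumulative incidence to Week 32 is 1 - exp(-0.20 × 224/365.25) = 11.5%. To Week 116 it is 1 - exp(-0.20 × 812/365.25) = 35.9%. No table in the available text estimates either quantity.

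**4. Who could reach Week 116?** Week 116 is Day 116 × 7 + 1 = 813, which is 812 days after first dose. No last-dose date is given, so the SAP date, 29 September 2020, serves as an outer bound: 29 September 2020 minus 812 days is 10 July 2018. If treatment ended by 31 May 2020, the month of the interim database lock, the date is 11 March 2018. Protocol Amendment 1, dated 30 January 2018, describes itself as preceding enrolment. That leaves an entry window of at most 161 days (23 weeks), or 40 days on the May date. Recruitment by date is not given, so that few if any subjects reached Week 116 is a strong inference, not a count.

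**The case against.** The windows are deliberate. SAP 2.7.1 says the aim is to see which AEs occur in which period, and it separates switched subjects up to Week 32 for a stated reason. The analysis is descriptive, no comparison of late with early percentages is announced, and the report is abbreviated for a programme stopped for lack of efficacy. Exposure thresholds (32, 40 and 44 weeks, 1 year, 56 weeks, 1.5 and 2 years) and discontinuation times will show truncation overall. The first window is close to fixed-length and little affected. AEs starting less than four weeks after last intake still count, so observation is not confined to days on drug.

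All of this is fair, and it is a reason to keep the windows. It does not supply the endpoint that Table 1-2 marks for the report, and the exposure table is neither split by window nor tied to AEs.

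A reader might infer more than the documents support:

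- *That the SAP contains no cumulative or exposure-based AE summary anywhere.* SAP 2.5.1 refers to section 2.8 for the extension's safety objective, and that section is not in the available text; nor is 2.7.4. The reference may be a slip for 2.7, but absence cannot be proved.
- *That the SAP carried over a fixed-follow-up statistic from the extension protocol.* That protocol was not available.
- *That the percentage could vary 18-fold.* At the same rate, 4 weeks of follow-up for everyone gives 1.5% and 84 weeks for everyone gives 27.5%. But these are two uniform extremes, and the dates make the second nearly unattainable.
- *That closure biases 30 mg against 50 mg.* A common calendar stop affects both doses alike. A bias would need different discontinuation, and the documents give no evidence of that.

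**Conclusion.** The point holds for the available SAP text. The extension's retained primary endpoint is not delivered by the AE tables in 2.7.1: there is no cumulative figure to Week 32, and Week 116 is replaced by an open-ended window whose percentage varies with follow-up. Under even spread, that variation is about 5-fold at 20 per 100 patient-years (3.0% to 14.5%) and 3.6-fold at 1 per patient-year (50.4/13.9).

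The size rests on a constant hazard and assumed rates. The SAP says follow-up is shorter than planned; that it is unequal between subjects is inferred from staggered entry and a common stop. This is a reporting gap that should be closed, not an error that invalidates the AE data.

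**What to change.** - Keep the three windows. In the Week 16-32 and post-Week-32 tables, add patient-years at risk and the exposure-adjusted incidence rate (subjects with a first event per 100 patient-years, 95% CI) for any AE, SAEs, AEs leading to discontinuation and common preferred terms.
- Add a cumulative summary from Day 1 to Week 32, and to the end of available follow-up, for subjects on 30 mg or 50 mg throughout.
- Show switched subjects separately, on a scale of time since first 30 mg or 50 mg dose. Pooling by study week would mix 32 weeks on these doses with 32 - 16 = 16.
- Restate the Week 116 endpoint as 'up to the last available exposure', add the number reaching Week 116 to the exposure table (its last threshold is 2 years), and record the change in SAP Section 4.
- Correct or confirm the reference in SAP 2.5.1 to section 2.8.

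The cost is SAP wording and a few more tables from dates already collected. The rates assume a roughly constant hazard, and the long-term safety claim becomes more modest.

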# 2.7.1.1 Adverse events of special interest / grouping of AEs

Summary tables showing the effects of ZPL389 in the core study on QTc and liver events will be produced following standard tables.

Additionally since part of the study was conducted during the COVID-19 pandemic, a listing of patients with suspected or confirmed SARS-COV-2 infection will be produced.

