3.5 Purpose and timing of interim analyses/design adaptations

An interim analysis may be performed to support decision making concerning the current clinical study or project. As a consequence the study sample size may be reduced, e.g. size of lower dose arms may be reduced by approximately 30%.

3.6 **Risks and benefits**

To date, 289 subjects (including asthma, psoriasis and AD patients and healthy volunteers) have been treated with at least one dose of ZPL389. The longest treatment duration to date occurred in a study of ZPL389 30 mg/day for 12 weeks in subjects with moderate to severe plaque psoriasis. In an ongoing study (CZPL389A2101), 75 healthy subjects received ascending single doses up to 400 mg ZPL389 and multiple doses of 50 mg/day and 100 mg/day for 21 days.

In the AD Phase 2a PoC study (N = 98), safety profile of ZPL389 (30 mg o.d.) was comparable to placebo and the percentages of subjects who reported adverse events were similar following 8 weeks of treatment with ZPL389 or placebo. The most common adverse events in the Phase 2a study were nasopharyngitis (12/65 [19%] subjects in the ZPL389 group and 8/33 [24%] subjects in the placebo group) and headache (7/65 [11%] subjects in the ZPL389 group and 4/33 [12%] subjects in the placebo group). No serious adverse events (SAEs) were reported following treatment with ZPL389.

Due to preclinical findings suggesting ZPL389 might prolong the corrected QT (QTc) interval when administered at several fold multiples of the intended clinical dose, 12-lead ECG monitoring was conducted in five completed clinical studies performed to date, and no clinically significant changes in ECG parameters including QTc interval prolongation have been observed following single doses of up to 48 mg and multiple doses of up to 50 mg o.d.

Interim analysis data from the ongoing study CZPL389A2101 showed clinically relevant increases of QTcF at single doses of 300 and 400 mg ZPL389 (plasma concentrations exceeding the concentration at Cmax,ss of a 50 mg o.d regimen). All elevations of QTcF and QT were asymptomatic. There were no QTcF or QT values \geq 500 msec and no changes in QTcF \geq 60 msec.

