8.4 Data Monitoring Committee

A DMC will review cumulative safety data at scheduled meetings. Of note, the clinical safety plan for this study includes close monitoring by the investigator for signs of abnormal cardiac and hepatic parameters, study entry criteria and treatment discontinuation criteria (Section 5.6).

The collection and summary of these data will be prepared by a designated CRO or Novartis.

Details on the organization and function of the DMC will be described in the DMC charter.

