After completing 100 weeks of study treatment during the extension study (i.e. up to Week 116 including 16 weeks of the core study), subjects were to enter the 4 weeks treatment-free follow-up period.

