# 3 Sample size calculation

The planned sample size for the core study was 360 subjects. Since the study was stopped early the final sample size will be less than this.

The sample size was determined with the software ADDPLAN DF, version 3.1.8, with settings for minimum power function and model based contrasts.

The sample size was derived to detect a dose-response with 90% power and a one-sided alpha of 2.5%. A placebo response rate of 10% was assumed. A maximum treatment effect for ZPL389 of 20%-points higher than placebo wass assumed. An unbalanced allocation ratio of 2:1:1:2:2 corresponding to treatment arms placebo: 3 mg: 10 mg: 30 mg: 50 mg, with more subjects allocated to placebo and the higher doses, was chosen to increase the precision of the estimate for the treatment effect at doses in the expected efficacious dose range.

Under these assumptions, a sample size of 360 subjects in total will be required, randomized to 90:45:45:90:90 subjects corresponding to placebo: 3 mg: 10 mg: 30 mg: 50 mg treatment arms.

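### The dedicated QTc and liver-event tables stop at the core study; after Week 16 the visible SAP counts these two risks only as individual adverse event terms

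*SAP*

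**What the plan says.** SAP 2.7.1.1, on adverse events of special interest, plans dedicated tables for two risks and confines them to the core study: "Summary tables showing the effects of ZPL389 in the core study on QTc and liver events will be produced following standard tables". It gives no reason for the limit.

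SAP Table 1-2 gives the extension's primary objective as "To assess the short-term and long- term safety of 30 mg o.d and 50 mg o.d ZPL389" and marks it for inclusion in the study report. The endpoint attached to it is "Frequency of AEs at Week 32 (short- term) and Week 116 (long-term". It names no QTc or liver endpoint.

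SAP 2.7.1 divides treatment-emergent AEs into three periods: the first 16 weeks, Weeks 16 to 32, and after Week 32. For Weeks 16 to 32 it separates subjects who moved up from placebo or a low dose from those already on 30 or 50 mg. After Week 32 it groups by 30 mg and 50 mg. Tables are by system organ class and preferred term, with severity, relatedness, serious events and events leading to discontinuation. SAP 2.7.3 brings in abnormal laboratory results only where they qualify as AEs.

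SAP 2.1 states that core and extension data will be presented together.

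**The concern.** QTc and liver are the two safety topics that the programme itself singles out. Protocol 3.6 reports that interim phase 1 data "showed clinically relevant increases of QTcF at single doses of 300 and 400 mg ZPL389", and describes liver monitoring as a precaution. Protocol 8.4 refers to "close monitoring by the investigator for signs of abnormal cardiac and hepatic parameters". Protocol 3.6 also says that the longest treatment before this trial was 12 weeks at 30 mg. In these documents, the extension is therefore the only source of exposure beyond 16 weeks.

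The parent section, SAP 2.7.1, is built to follow AEs past Week 16, yet the special-interest tables do not use that structure. What is at stake is a grouped, threshold-based view of QTc and liver findings in two sets of subjects: those exposed longest to 30 or 50 mg, and those who first reached these doses in the extension.

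**Working it through.** The plan gives no figure to reproduce on this point. The check is whether the AE tables already do the work of the missing ones, followed by simple arithmetic for scale.

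**Do the AE tables fill the gap?**

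1. Protocol 7.3 requires liver laboratory triggers and liver events to be considered whether or not they are reported as AEs. Table 14-1 defines most of them by multiples of the upper limit of normal for ALT, AST, ALP and bilirubin.
2. Protocol 7.5 defines a notable QTcF by threshold: at least 450 msec in men, at least 470 msec in women, or a 30 msec increase from baseline.
3. Protocol 7.1 makes an abnormal test result an AE only if it causes signs or symptoms, is judged clinically significant, or needs therapy.
4. SAP 2.7.3 carries laboratory abnormalities into the AE tables only when they meet AE criteria.

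Points 1 and 2 define threshold findings that need not satisfy point 3. A subject with such a finding after Week 16 and no reported AE is in none of the summary tables that can be read. Findings that are reported as AEs are counted, but spread over separate preferred terms. Some Table 14-1 liver events, such as jaundice, are clinical and would be reported as AEs anyway, so the gap concerns the laboratory-defined ones.

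This reasoning assumes that the extension uses the core protocol's thresholds and AE rule. The extension protocol is not among the documents.

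**Scale, on planned numbers**

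Inputs:
- Core allocation: "a sample size of 360 subjects in total will be required, randomized to 90:45:45:90:90 subjects" (SAP 3), in the order placebo, 3, 10, 30, 50 mg.
- Placebo, 3 mg and 10 mg subjects entering the extension "would be randomized to receive ZPL389 30 mg o.d. or 50 mg o.d. in a 1:1 ratio" (SAP 1.1).
- Extension size 202 to 230; core 16 weeks, extension 100 weeks (SAP 1.1).

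Results:
- Subjects whose 30 or 50 mg exposure could come only in the extension: (90 + 45 + 45)/360 = 180/360 = 50%. This is a ceiling, reached only if all of them enter.
- Planned entry: 202/360 = 56% to 230/360 = 64%. If entry is proportional across arms (an assumption), switchers are half of that, about 28% to 32% of randomized subjects.
- Core share of planned treatment time: 16/116 = 13.8%.
- Planned 30 or 50 mg exposure, assuming no dropout within a period: core 180 × 16 = 2,880 subject-weeks; extension 202 × 100 = 20,200 to 230 × 100 = 23,000.
- Share inside core-only tables: 2,880/(2,880 + 20,200) = 12.5%, down to 2,880/(2,880 + 23,000) = 11.1%.

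These are planned figures. SAP 1.1 says that the final number of patients and the follow-up per patient are below plan and does not say by how much, so the realized shares cannot be computed.

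**The case against.** The strongest reply is that the extension's safety objective is already analysed. Its stated endpoint is AE frequency, and SAP 2.7.1 delivers that for both later periods, with switchers to 30 mg and to 50 mg shown separately for Weeks 16 to 32. Clinically significant QT or hepatic findings should be reported as AEs and so be counted. This stands. It rules out the stronger reading a reader might infer, that QTc and liver risks go unsummarized where exposure is longest or that the primary objective has no analysis. It does not reach threshold crossings without a reported AE, or the lack of any grouping.

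Second, absence cannot be fully shown. The SAP contents list a section 2.7.4 on other safety data whose text is not available and which may cover ECGs. SAP 2.5.1 also points to a section 2.8 for the extension's safety objective, and that text is not visible either. This stands as a caveat, mainly for QTc. For liver, the laboratory section (2.7.3) can be read and covers only results that qualify as AEs.

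Third, core-only tables can be defended. Only the core has a concurrent placebo arm, the report is abbreviated, and SAP 2.3.1 expects disposition in the extension to differ from what was intended. The SAP does not give this as its reason. The argument bears on how later tables should be labelled and read. It is not a reason to omit them.

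Fourth, the signals are modest. The QTcF increases were at single doses of 300 and 400 mg. For 50 mg once daily, Protocol 3.6 reports an upper 90% confidence bound below 10 msec, and it describes no preclinical liver toxicity signal. This lowers the urgency. The two risks remain the ones that the SAP itself selected for special tables.

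**Conclusion.** The point holds in a limited form. The dedicated QTc and liver-event tables are confined to the core study without a stated reason. In the visible plan, subjects who cross a laboratory liver threshold or a notable-QTcF threshold after Week 16 without a reported AE appear in no summary table. The extension's retained primary objective therefore has its AE-frequency endpoint but no grouped or threshold-based summary of the two named risks.

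A reader might also infer that half of all randomized subjects lose their first high-dose exposure from these tables. The documents do not support that. The 50% is a ceiling from planned allocation; entry was optional, SAP 2.1 lists sequences that did not participate, and both studies stopped early. The actual share is lower and unknown. The 11% to 12% core share of planned 30 or 50 mg exposure likewise holds only for the original plan.

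The conclusion assumes that the unseen text, SAP 2.7.4 above all for QTc, does not already supply the tables, and that the core protocol's thresholds apply in the extension. No efficacy conclusion or error rate is affected.

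**What to change.** In SAP 2.7.1.1, delete the words that confine the sentence to the core study. Produce the same standard QTc and liver tables for Weeks 16 to 32 and after Week 32, with the treatment groups that SAP 2.7.1 already defines for those periods. Label the later tables as descriptive, because there is no concurrent placebo after Week 16. If the sponsor prefers to keep the restriction, state the reason in 2.7.1.1. If SAP 2.7.4 already covers post-Week-16 ECG data, a cross-reference to it would be enough for QTc.

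This is a cheap improvement. It uses standard tables, and the periods and groups are already defined. The downside is a few extra tables in an abbreviated report, with small numbers in the later periods that should be read with caution.
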